7.1.2 Adverse Events of Special Interest

In this study, the following adverse events are to be reported to BMS, regardless of whether these reports are classified as serious or unexpected:

1. liver test abnormalities accompanied by jaundice or hyperbilirubinemia
2. opportunistic infections associated with the use of saxagliptin, and
3. pancreatitis
4. anaphylaxis
5. angioedema and
6. Stevens’ Johnson syndrome.

7.1.3 Nonserious Adverse Events

Nonserious adverse events are all adverse events that are not classified as SAEs.

7.2 Assignment of Adverse Event Intensity and Relationship to Investigational Product

All adverse events, including those that are serious, will be graded by the investigator as follows:

7. Mild (Grade 1): awareness of event but easily tolerated
8. Moderate (Grade 2): discomfort enough to cause some interference with usual activity
9. Severe (Grade 3): inability to carry out usual activity
10. Very Severe (Grade 4): debilitating; significantly incapacitates subject despite symptomatic therapy.

The following categories and definitions of causal relationship to investigational product as determined by a physician should be used:

11. **Related:** There is a reasonable causal relationship to investigational product administration and the adverse event.
12. **Not Related:** There is not a reasonable causal relationship to investigational product administration and the adverse event.

The expression “reasonable causal relationship” is meant to convey in general that there are facts (eg, evidence such as de-challenge/re-challenge) or other arguments to suggest a positive causal relationship.

7.3 Collection and Reporting

Adverse events can be spontaneously reported or elicited during open-ended questioning, examination, or evaluation of a subject. To prevent reporting bias, subjects should not be questioned regarding the specific occurrence of one or more adverse events.

If known, the diagnosis of the underlying illness or disorder should be recorded, rather than its individual symptoms. The following information should be captured for all AEs: onset, duration, intensity, seriousness, relationship to investigational product, action taken, and treatment required. If treatment for the event was administered, it should be recorded in the medical record. The investigator must supply BMS and the IRB/IEC with any additional information requested, notably for reported deaths of subjects.

7.3.1 Serious Adverse Events and Adverse Events of Special Interest

Following the subject’s written consent to participate in the study, all SAEs and all AEs of Special Interest (defined in Section 7.1.2), whether related or not related to study drug, must be collected, including those thought to be associated with protocol-specified procedures. All SAEs must be collected that occur during the screening period and within 30 days of discontinuation of dosing. If applicable, SAEs must be collected that relate to any later protocol-specified procedure (eg, a follow-up skin biopsy). The investigator should report any SAE occurring after these time periods that is believed to be related to study drug or protocol-specified procedure.

An SAE report should be completed for any event where doubt exists regarding its status of seriousness.

If the investigator believes that an SAE is not related to study drug, but is potentially related to the conditions of the study (such as withdrawal of previous therapy, or a complication of a study procedure), the relationship should be specified in the narrative section of the SAE Report Form.

All SAEs, whether related or unrelated to saxagliptin, and all pregnancies must be reported to BMS (by the investigator or designee) within 24 hours of study personnel becoming aware of the event. If only limited information is initially available, follow-up reports are required. The original SAE form must be kept on file at the study site.

All SAEs should be reported via confirmed facsimile (fax) transmission, or scanned and reported via electronic mail to:

SAE Email Address: [contact]

SAE [contact]

For studies conducted under an **Investigator IND**, any event that is both serious and unexpected must be reported to the Food and Drug Administration (FDA) as soon as possible **and no later than 7 days** (for a death or life-threatening event) **or 15 days** (for all other SAEs) **after the investigator's or institution's initial receipt of the information.** The investigator must provide BMS with a copy of all adverse events filed with the FDA. SAEs should be reported on MedWatch Form 3500A, which can be accessed at: <http://www.accessdata.fda.gov/scripts/medwatch/>.

MedWatch SAE forms should be sent to the FDA at:

MEDWATCH

[name]

[name]

Fax: [name] ([name])

<http://www.accessdata.fda.gov/scripts/medwatch/>

All SAEs should simultaneously be faxed or e-mailed to BMS at:

Global Pharmacovigilance & Epidemiology

Bristol-Myers Squibb Company

[contact]

Email: [contact]

If an ongoing SAE changes in its intensity or relationship to study drug or if new information becomes available, a follow-up SAE report should be sent within 24 hours to BMS using the same procedure used for transmitting the initial SAE report.

All SAEs should be followed to resolution or stabilization. All pregnancies must be followed to outcome.

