and above. At the 5 mg dose, the mean decrease was approximately 100 cells/ μ L relative to placebo (from baseline absolute lymphocyte count of approximately 2200 cell/ μ L) based on a pooled analysis of the 5 placebo-controlled clinical studies including saxagliptin as monotherapy, and as add-on therapy to metformin, TZD and SU. While the clinical significance of the decreases in lymphocyte count relative to placebo is not known, the decreases were not associated with clinically relevant AEs.

Platelet counts: Results from the Phase 3 clinical studies demonstrated no clinically meaningful or consistent effect on platelet counts.

In the five-pooled monotherapy and placebo-controlled combination studies, the frequencies of AEs in the system organ class (SOC) Infection and Infestations were comparable in the saxagliptin 2.5 mg, saxagliptin 5 mg, and placebo groups (36.4%, 35.9%, and 34.8% respectively); a higher frequency of AEs was observed in the saxagliptin 10 mg group (40.1%). There was no evidence for an association of saxagliptin treatment with an increased risk of elevated liver function tests or serum creatinine.

Effect on QTc interval: In the clinical pharmacology program, results from a thorough QTc study at daily doses of saxagliptin up to 40 mg QD and analyses from other studies at daily doses up to 400 mg QD demonstrated an absence of an effect of saxagliptin and BMS-510849 on QTc interval in humans.

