5.3 Method of Assigning Subjects to a Treatment

Patients will be randomized to one of the two treatment groups i.e. saxagliptin or placebo. Randomisation numbers (patient numbers) will be assigned strictly sequentially

as patients become eligible for randomisation. Randomization will be computer-generated by the research pharmacy, and the investigators will be blinded to the treatment assignments. The research pharmacy will provide the randomisation number and the appropriate bottle numbers.

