8.2 Population for analysis

All patients used in the analyses of the primary and secondary objectives will belong to the intention-to-treat (ITT) population. This population is defined as all randomised patients. The patients will be analysed according to the treatment group to which they were randomized.

8.3 Endpoint Definitions:

Primary Efficacy Endpoint: is defined as the effect of saxagliptin compared with placebo on reduction in hepatic and myocardial fat.

Secondary Efficacy endpoint: is defined as the effect of saxagliptin compared with placebo on improvement in left ventricular systolic and diastolic function and a reduction in monocyte inflammation.

Safety endpoints: The number and percent of patients with an AE will be summarised for each treatment group. In addition, the number and percent of patients with a predefined marked abnormality in clinical laboratory tests will be summarised by treatment group.

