8.4.3 Safety Analysis

Safety is evaluated by the following endpoints:

o Incidence of overall AEs and AEs of special interest

Other safety endpoints:

o Changes from baseline in laboratory tests, pulse, BP, and body weight.

o Incidence of hypoglycaemic events.

9. Compliance with the Protocol and Protocol Revisions

The study must be conducted as described in the final IRB/IEC-approved protocol. Documentation of approval, signed by the IRB/IEC chairperson or designee, must be sent to the BMS protocol manager.

All protocol amendments and revisions to the informed consent must be submitted to the BMS protocol manager and to the IRB/IEC. No protocol amendments will be implemented until written approval has been given by the IRB/IEC, except when necessary to eliminate an immediate hazard to study subjects. Administrative letters should also be sent to the BMS protocol manager and IRB/IEC; however, they do not require approval.

If a deviation or change to a protocol is implemented to eliminate an immediate hazard(s) prior to obtaining IRB/IEC approval/favorable opinion, as soon as possible the deviation or change must be submitted to:

- IRB/IEC for review and approval/favorable opinion
- Bristol-Myers Squibb
- Regulatory Authority(ies), if required by local regulations.

Documentation of approval signed by the chairperson or designee of the IRB(s)/IEC(s) must be sent to BMS.

If an amendment substantially alters the study design or increases the potential risk to the subject: (1) the consent form must be revised and submitted to the IRB(s)/IEC(s) for review and

approval/favorable opinion; (2) the revised form must be used to obtain consent from subjects currently enrolled in the study if they are affected by the amendment; and (3) the new form must be used to obtain consent from new subjects prior to enrollment.

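### One of the six adverse events of special interest is defined by attribution to saxagliptin, which conflicts with the collection rule in 7.3.1 and filters the incidence reported under 8.4.3

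*Combined protocol and SAP*

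**What the plan says.** Section 7.1.2 lists six events of special interest and states that "the following adverse events are to be reported to BMS, regardless of whether these reports are classified as serious or unexpected". That sentence sets aside seriousness and expectedness; it does not mention relatedness. Five of the items are named by the event alone: liver test abnormalities with jaundice or hyperbilirubinemia, pancreatitis, anaphylaxis, angioedema and Stevens-Johnson syndrome. Item 2 is "opportunistic infections associated with the use of saxagliptin".

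Section 7.3.1 starts collection once consent is signed and requires that "all AEs of Special Interest (defined in Section 7.1.2), whether related or not related to study drug, must be collected".

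Section 8.4.3 names as a safety endpoint "Incidence of overall AEs and AEs of special interest". The presentation by arm comes from the safety paragraph of 8.3: "The number and percent of patients with an AE will be summarised for each treatment group". Neither section states a test between arms. Section 7.2 has every adverse event rated as related or not related to the investigational product, and 7.3 has that rating captured for all adverse events.

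**The concern.** A safety endpoint should be defined by what happened to the patient, with the opinion about cause kept as a separate variable. Item 2 makes the opinion part of the definition. The rule in 7.3.1 expressly covers unrelated events, but for this item an unrelated event is not on the list, so that half of the rule has nothing to act on.

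Three things are at stake:

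- the count of opportunistic infections in the special-interest summary, which would depend on an investigator's attribution;
- the special report to BMS for nonserious infections judged unrelated;
- consistency across the list, since the other five items are counted without any such filter.

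Infection is also a topic on which the sponsor has chosen to keep watch. Section 1.1.3.1 reports a mean lymphocyte decrease of about 100 cells/µL relative to placebo at 5 mg, the dose used here.

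**Working it through.** The plan states no figure for this endpoint, so there is none to reproduce. The check is a comparison of the text, followed by a short calculation of how the filter acts.

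**1. Does item 2 conflict with 7.3.1?**

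| Source | Rule |
|---|---|
| 7.1.2, items 1 and 3 to 6 | Event alone |
| 7.1.2, item 2 | Event plus association with saxagliptin use |
| 7.3.1 | Collect from consent, related or not, using the 7.1.2 definition |

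Read causally, item 2 admits only infections attributed to the drug, while 7.3.1 requires unrelated ones as well. The timing conflicts too. In the Time and Events Schedule (6.1), consent is at week -4 and study drug starts at week 0. An infection in those four weeks falls inside the collection window of 7.3.1 but cannot be associated with use of a drug not yet taken.

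**2. What happens to the count in 8.4.3?**

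Let p_S and p_P be the true 26-week risks of opportunistic infection on saxagliptin and placebo. Let a be the share of such infections that the investigator attributes to study drug. Section 5.3 says "the investigators will be blinded to the treatment assignments", so a is taken to be the same in both arms. This is an assumption.

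- Expected incidence shown: a × p_S and a × p_P.
- Share of true events missing in each arm: 1 - a.
- Difference shown: a × (p_S - p_P).

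The documents give neither p nor a. For illustration:

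| a (assumed) | Share missing in each arm |
|---|---|
| 0.75 | 25% |
| 0.50 | 50% |
| 0.25 | 75% |

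Under blinded attribution the filter lowers both arms and shrinks any real difference towards zero. It does not create a difference where there is none.

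**3. What is still captured?**

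Section 7.3.3 has all identified nonserious events recorded on the case report form. Section 7.3.1 has every serious event collected and reported to BMS whether related or not. An on-treatment infection that fails item 2 therefore still enters the overall adverse event incidence. What it loses is its place in the special-interest summary and, if nonserious, the report to BMS under 7.1.2.

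**4. Does the qualifier add information?**

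No. Relatedness is already rated under 7.2 and captured under 7.3 for every adverse event.

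**The case against.** The best defence is that the qualifier is temporal. The general definition in 7.1 describes an adverse event as associated in time with use of the product, whether or not thought related, and 7.2 uses different words for causality. On that view item 2 simply means an opportunistic infection while on study drug. This does not remove the conflict. Every adverse event under 7.1 already has that temporal link, so the qualifier does any work only if it is causal. A temporal reading would also still exclude the period between consent and first dose, which 7.3.1 includes.

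A second objection is that little is lost. This stands: on-treatment infections remain in the database with a relatedness rating, so the full count could be rebuilt.

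A third is that the background evidence is weak. This also stands. In 1.1.3.1 the higher infection frequency (40.1%) is at 10 mg, which is not used here; 5 mg and placebo are called comparable (35.9% and 34.8%), and the lymphocyte decreases were not linked to clinically relevant events. None of these figures concerns opportunistic infection. The point rests on the inconsistent definition and not on a demonstrated risk.

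In the other direction, a reader might infer that placebo infections can never count, so that the placebo incidence is zero by construction and background infections look like a drug effect. The documents do not support that as the expected outcome:

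- Attribution is made blind, so a placebo infection can be attributed to study drug and counted.
- The protocol uses the drug's name for the blinded product elsewhere: 5.1 names it as the investigational product, 7.3.1 uses it when requiring reports of all serious events, and 7.5.1 uses it for pregnancy testing of all women of childbearing potential.
- No section calls for events to be reclassified after unblinding.
- Section 8.4.3 states no comparison between arms; the summary by arm in 8.3 is descriptive.

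**Conclusion.** The inconsistency is real and minor. It affects one of six events of special interest. Followed as written, item 2 turns that part of the safety endpoint into a count of infections the investigator attributes to the drug. It loses a share 1 - a in each arm and drops nonserious unrelated infections from the special reports to BMS. The size in events is unknown because neither the infection rate nor the attribution share is given; equal attribution in the two arms is assumed from the blinding.

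A zero placebo count follows only if item 2 is applied literally to actual exposure. On that reading, with 20 placebo patients (40 enrolled, equal allocation assumed), the chance that at least one placebo event is discarded is 1 - (1 - p)^20: 2% at p = 0.1%, 18% at 1%, 33% at 2% and 64% at 5%. Each p is an assumption without support in the documents, and the conclusion does not depend on these figures. The primary analysis, the sample size and the overall adverse event incidence are unaffected.

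**What to change.** In item 2 of 7.1.2, delete the six words that follow the name of the event, so that any opportunistic infection in either arm qualifies and the item agrees with 7.3.1. In 8.4.3, add one sentence: events of special interest are summarised by treatment group as number and percent of patients, regardless of investigator causality, with the related/not-related rating from 7.2 shown separately.

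No new data collection is needed, since the rating is already captured. The cost is one wording change, one added sentence and possibly a few more reports of unrelated infections to BMS.

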7.3.2 Handling of Expedited Safety Reports

In accordance with local regulations, BMS will notify investigators of all SAEs that are suspected (related to the investigational product) and unexpected (ie, not previously described in the Investigator Brochure). In the European Union, an event meeting these criteria is termed a Suspected Unexpected Serious Adverse Reaction (SUSAR). BMS will send investigators an expedited safety report (ESR) to notify them of such an event.

Other important findings that BMS may report as ESRs include increased frequency of a clinically significant expected SAE, an SAE considered associated with study procedures that could modify the conduct of the study, lack of efficacy that poses significant hazard to study subjects, clinically significant safety findings from a nonclinical (eg, animal) study, important safety recommendations from a study data monitoring committee, or the decision by BMS to end or temporarily halt a clinical study for safety reasons.

Upon receiving an ESR from BMS, the investigator must review and retain the ESR with the Investigator Brochure. Where required by local regulations or when there is a central IRB/IEC for the study, BMS will submit the ESR to the appropriate IRB/IEC. The investigator and IRB/IEC will determine if the informed consent requires revision. When BMS has a written agreement with a local IRB/IEC, BMS will directly submit ESR(s). The investigator should also comply with the IRB/IEC procedures for reporting any other safety information.

In addition, BMS will report suspected serious adverse reactions (whether expected or unexpected) to the relevant health authorities in all concerned countries according to local regulations (either as expedited and/or in aggregate reports).

7.3.3 Nonserious Adverse Events

The collection of nonserious AE (NSAE) information should begin at initiation of study drug. NSAE information should also be collected from the start of a placebo lead-in period or other observational period intended to establish a baseline status for the subjects.

NSAEs should be followed to resolution or stabilization, or reported as SAEs if they become serious (see Section 7.3.1). Follow-up is also required for NSAEs that cause interruption or discontinuation of study drug, or those that are present at the end of study treatment as appropriate. All identified NSAEs must be recorded and described on the NSAE page of the CRF.

Completion of supplemental CRFs may be requested for AEs and/or laboratory abnormalities that are reported/identified during the course of the study.

7.4 Laboratory Test Abnormalities

All laboratory test results captured as part of the study should be recorded following institutional procedures. When reporting a test result that constitutes an adverse event, the clinical term should be used; for example, the event should be reported as “anemia” not “low hemoglobin.” Test results that constitute SAEs should be documented and reported as such.

The following laboratory abnormalities should be captured on the NSAE CRF page or SAE Report Form as appropriate:

- Any laboratory test result that is clinically significant or meets the definition of an SAE.
- Any laboratory abnormality that required the subject to have study drug discontinued or interrupted.
- Any laboratory abnormality that required the subject to receive specific corrective therapy.

7.5 Pregnancy

WOCBP must use an effective method of birth control during the course of the study, in such a manner that the risk of failure is minimized.

7.5.1 Requirements for Pregnancy Testing

All WOCBP MUST have a negative pregnancy test within 72 hours before receiving saxagliptin. The minimum sensitivity of the pregnancy test must be 25 IU/L or equivalent units of HCG. If the pregnancy test is positive, the subject must not receive saxagliptin and must not continue in the study.

In addition, all WOCBP must be instructed to contact the investigator and/or other study personnel immediately if they suspect they might be pregnant (eg, missed or late menstrual period) at any time during study participation.

7.5.2 Reporting of Pregnancy

If, following initiation of the investigational product, it is subsequently discovered that a study subject is pregnant or may have been pregnant at the time of investigational product exposure, including during at least 6 half-lives after product administration, the investigational product will be permanently discontinued in an appropriate manner (eg, dose tapering if necessary for subject safety). Protocol-required procedures for study discontinuation and follow-up must be performed on the subject unless contraindicated by pregnancy (eg, x-ray studies). Other appropriate pregnancy follow-up procedures should be considered if indicated.

The investigator must immediately notify the BMS Medical Monitor of this event and complete and forward a Pregnancy Surveillance Form to BMS within 24 hours and in accordance with SAE reporting procedures described in Section 7.3.1

Follow-up information regarding the course of the pregnancy, including perinatal and neonatal outcome and, where applicable, offspring information must be reported on the Pregnancy Surveillance Form.

Any pregnancy that occurs in a female partner of a male study participant should be reported to the sponsor. Information on this pregnancy will be collected on the Pregnancy Surveillance Form.

7.6 Overdose

An overdose is defined as the accidental or intentional administration of any dose of a product that is considered both excessive and medically important. All occurrences of overdose must be reported as an SAE (see Section 7.3.1 for reporting details).

Once-daily, orally administered saxagliptin has been shown to be safe and well tolerated, with no clinically meaningful effect on QTc interval or heart rate at doses up to 400 mg daily for 2 weeks (80 times the recommended human dose). In the event of an overdose, appropriate supportive treatment should be initiated as dictated by the patient's clinical status. Saxagliptin and its major metabolite are removed by hemodialysis (23% of dose over 4 hours).

